4.1.1 Analysis Population

- Intent-to-treat (ITT) population: The Intent-to-treat population is defined as all randomized subjects who received at least one dose of study treatment (aducanumab or placebo).
- Per-protocol (PP) population:

The per-protocol population is defined as all subjects in the ITT population and also

- o had no violations of the following inclusion criteria:
 - Must have at least 6 years of education or work experience to exclude mental deficits other than MCI or mild AD;
 - Must have a positive amyloid PET scan;
 - Must have:
 - A CDR-Global Score of 0.5;
 - A Repeatable Battery for Assessment of Neuropsychological Status (RBANS) score of 85 or lower indicative of objective cognitive impairment (based upon the Delayed Memory Index score);
 - An MMSE score between 24 and 30 (inclusive).
- o had at least 14 infusions.
- o did not make any change to concomitant AD symptomatic medications during the study.

Final V1.0

- ¹⁸F-florbetapir amyloid PET analysis population:
 - The ¹⁸F-florbetapir amyloid PET analysis population is defined as all randomized subjects who received at least one dose of study treatment (aducanumab or placebo), used ¹⁸F-florbetapir ligand for amyloid PET scan, and had an evaluable baseline amyloid PET SUVR value for the composite region-of-interest using cerebellum as the reference region.
- ¹⁸F-flutemetamol amyloid PET analysis population (applicable only to Japan): The ¹⁸F-flutemetamol amyloid PET analysis population is defined as all randomized subjects who received at least one dose of study treatment (aducanumab or placebo), used ¹⁸F-flutemetamol ligand for amyloid PET scan, and had an evaluable baseline amyloid PET SUVR value for the composite region-of-interest using cerebellum as the reference region.

• Safety population:

The safety population is defined as all randomized subjects who received at least one dose of study treatment (aducanumab or placebo). It is the same population as the ITT population.

• Safety MRI population:

The safety MRI population is defined as all randomized subjects who received at least one dose of study treatment (aducanumab or placebo) and had at least one post-baseline MRI assessment.

• PK analysis population:

The PK analysis population is defined as all randomized subjects who received at least one dose of study treatment (aducanumab or placebo) and had at least one measurable aducanumab concentration in serum.

• Immunogenicity population:

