4.5 Safety Analysis

4.5.1 General Considerations

Analysis population

Safety population will be used for safety analyses of AEs, clinical laboratory data, Columbia Suicide Severity Rating Scale (C-SSRS) data, ECG data and vital sign data (all the safety data except for ARIA data). Safety MRI population will be used for analyses of ARIA data.

Final V1.0

Safety treatment groups

Different from the randomization treatment groups, if a subject who was randomized to placebo group accidentally received one or more doses of the active treatment during the study, he/she will be classified as either low or high dose group for all the safety analyses, depending on the ApoE status and the maximal dose level of the active treatment received (Table 5). A listing of such subjects will be provided, as described in section 4.2.5. Safety treatment groups will be the same as the randomization treatment groups for other subjects (subjects randomized to active treatment groups, and subjects randomized to placebo without any accidental active dose). Safety treatment groups will be used for all the safety analyses unless otherwise specified.

Table 5: Safety treatment groups for placebo subjects with accidental active treatment

Randomization treatment group	Randomization ApoE status	Safety treatment group classification based on the maximum dose level of the accidental active treatment		
		>0 to 3 mg/kg	>3 to 6 mg/kg	>6 mg/kg
Placebo	ΑροΕ ε4 (+)	Low dose	High dose	High dose
	ΑροΕ ε4 (-)	Low dose	Low dose	High dose

Safety analysis displays

AEs, clinical laboratory data, C-SSRS data, ECG data and vital sign data (all the safety data except for ARIA data) will be summarized by treatment group (placebo, low dose, high dose and BIIB037 total; analysis display A in Appendix 6.1), unless otherwise specified. All the ARIA related tables will be presented by treatment group stratified by ApoE status (3 columns under each treatment group: ApoE ϵ 4+, ApoE ϵ 4- and total; analysis display B in Appendix 6.1), unless otherwise specified. A subset of AE tables will also be presented by treatment group stratified by ApoE status in addition to by treatment group. All the listings will be presented by treatment group stratified by ApoE status.

Incidence, incidence proportion and incidence rate

Incidence and incidence proportion will be provided in incidence tables. Incidence is
defined as the number of subjects who experienced an event. Incidence proportion is

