6.2 Protocol Deviation Classification

Deviation Category	Deviation Description	Severity Classification
Administrative criteria	Study team member performing study assessments without being authorized as per delegation log.	Minor
Administrative criteria	Unblinded information made available to the blinded CRA.	Major
Administrative criteria	Unblinded information made available to the blinded site personnel.	Major
Administrative criteria	Incorrect version of any assessments used	case by case
Administrative criteria	Filing issues misfiling of documents	N/A
Administrative criteria	Correction of source data not compliant with GCP	N/A
Administrative criteria	Sharing of account credentials between raters on the MedAvante Virgil tablet/Portal, or sharing of accounts on any study system	Major
Concomitant Medications	Administration of any vaccination/booster should be given < 10 days prior to any dosing visit or 10 days after a dosing visit.	Minor
Concomitant Medications	Administration of any disallowed concomitant therapy to the subject.	Major
Concomitant Medications	Change of medications that subjects were receiving at enrollment or start of new medications or herbal preparations during the study period, without consultation with the investigator and review with the Medical Monitor	Case by case basis
Concomitant Medications	Change in AD medications during course of the study.	Minor
Eligibility and Entry criteria	Any "no" response to inclusion criteria and/or any "yes" response to exclusion criteria and subject was subsequently randomized for criteria.	Major
Eligibility and Entry criteria	Any eligibility assessment not performed.	Major
Eligibility and Entry criteria	Any eligibility assessment performed after the randomization of the patient (including lab samples), and subject is ineligible based upon assessment.	Major
Eligibility and Entry Criteria	Exclusionary lab value results but subject was dosed.	Major
Eligibility and Entry criteria	Subject not eligible based on scores of CDR, MMSE, RBANS DMI, as defined by inclusion criterion #6.	Major
Eligibility and Entry criteria	Subject on allowed chronic medications that have not been stable for at least 4 weeks prior to Screening V1 or use of AD medications at doses that have not been stable for at least 8 weeks prior to Screening V1.	Major

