Informed Consent	Subject/informant/legally authorized representative did not sign Main ICF, PET ICF, and/or Substudy ICFs (and substudy procedures were conducted). Not clear on the ICF who has been signing the document (patient or legal representative).	Major
Informed Consent	Principal Investigator / individual obtaining consent did not sign Main ICF, PET ICF, and/or Substudy ICFs (and substudy procedures were conducted).	Major
Informed Consent	Not clear on the the ICF who has been signing the document (patient or legally authorized representative).	Major
Informed Consent	ICF signed by either only patient or only care giver/legally authorized representative, when ICF should have been signed by both.	Major
Informed Consent	Incorrect or outdated version of Main ICF, PET ICF, and/or Substudy ICFs signed by subject/informant/legally authorized representative.	Major
Informed Consent	IEC/IRB contact details or site's contact details not included on ICF.	Minor
Informed Consent	Incorrect completion of ICF (i.e., subject/study partner/LAR/person obtaining consent did not provide date of signature; subject/study partner/LAR/person obtaining consent noted incorrect date of signature; subject/study partner/LAR/person obtaining consent printed name when should have signed, subject/study partner/LAR/person obtaining consent signed on line for printed name, printed name on line for signature, etc.)	Minor
Informed Consent	Site personnel who signed ICF is not on Site Personnel Signature Delegation Log and/or not authorized by PI to sign ICF	Major
Informed Consent	No evidence (source documentation) that Informed Consent was obtained from the study subject / study partner.	Major
Informed Consent	ICF obtained by subject is not in subject's native language.	Major
Informed Consent	Protocol specific procedures such as physical exam, medical history, neurological history, ECGs, rater scales, lab tests, blood draws, including first study drug dose performed prior to the date of the consent.	Major
Informed Consent	Subject and/or Study Partner/Caregiver not signing ICFs at time of reconsent.	Major
Informed Consent	Untimely reconsenting of subject/caregiver on newly approved ICFs.	Major
Investigational Product Compliance	IP storage temperature out of range and site used IP without confirmation from Biogen regarding usability	Case by case basis
Investigational Product Compliance	Incorrect cohort IP dispensed to subject	Major

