Laboratory assessments criteria		Minor			
Laboratory assessments criteria	Lab specimens temperature log is not being maintained nor checked by applicable study personnel.				
Laboratory assessments criteria	Use of incorrect lab kit.				
Laboratory assessments criteria	PBMC not collected, or not collected within protocol specified time.				
Other	Site repeatedly commits same minor deviations.				
Randomization criteria	Subject recorded as randomized in IXRS by mistake but not dosed.	Major			
Randomization criteria	Subject randomized to wrong arm due to mis-entry of ApoE ε4 carrier status.				
Regulatory or Ethics Approval Criteria	No evidence that IRB / CEC / LEC approved the final protocol.	Major			
Regulatory or Ethics Approval Criteria	No evidence that IRB / CEC / LEC was notified of protocol amendments in a timely manner.	Minor			
Regulatory or Ethics Approval Criteria	Failure to notify or obtain approval from the IRB / CEC / LEC of a change of investigator.	Minor			
Regulatory or Ethics Approval Criteria	Failure to obtain or keep updated regulatory authorization to conduct a study.	Major			
Regulatory or Ethics Approval Criteria	Failure to obtain IRB / CEC / LEC approval of a subject directed document (e.g., subject questionnaires, advertisements, etc.)	Major			
Regulatory or Ethics Approval Criteria	Failure in Safety Reporting as per local requirements (SUSARS, line listings, progress reports, etc.)				
Serious Adverse Event Criteria	SAEs not appropriately reported (i.e., reported as an AE when SAE criteria have been met, or SAE not reported within 24 hours).				
Serious Adverse Event Criteria	Pregnancies not appropriately reported within 24 hours of study site staff becoming aware of the pregnancy.				
Serious Adverse Event Criteria	Adverse Events of Special Interest not reported within 72 hours following the receipt of abnormal MRI findings from the central MRI reader.				
erious Adverse Event Criteria SAEs not appropriately reported to the IRB/EC.					
Study Procedures criteria	Inconsistent rater used for primary, secondary endpoints	Major			

Study Procedures criteria	CDR raters were performing other assessments on subjects they performed CDRs for.	Major			
Study Procedures criteria	Secondary endpoint assessments raters were performing other assessments on subjects they performed these assessments for.	Major			
Study Procedures criteria	MOCA was administered by a rater rather than the treating HCP.	Major			

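### The per-protocol set counts infusions without requiring the assigned product, so a placebo subject given active drug can be analysed as per-protocol placebo

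*SAP*

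**What the plan says.** All references are to the placebo-controlled SAP.

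- **Per-protocol definition (4.1.1).** An ITT subject qualifies if he or she "had no violations of the following inclusion criteria" (education or work experience, positive amyloid PET, and the CDR, RBANS and MMSE entry ranges), "had at least 14 infusions", and "did not make any change to concomitant AD symptomatic medications during the study". Nothing is said about which product was infused.
- **Grouping (4.3.1, 4.3.2.3.2).** Efficacy is presented by randomized group. The per-protocol analysis reuses the primary MMRM in the per-protocol population.
- **Placebo subjects given active drug (4.2.5, 4.5.1).** Section 4.2.5 promises a listing of their dosing records. Section 4.5.1 provides that "if a subject who was randomized to placebo group accidentally received one or more doses of the active treatment during the study", the subject is classed as low or high dose for the safety analyses, according to ApoE status and the highest active dose received.
- **Deviation log (4.2.4, Appendix 6.2).** "Incorrect cohort IP dispensed to subject" is rated Major. Major deviations are summarized by treatment group and listed. No rule connects them to the per-protocol set.

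**The concern.** A per-protocol analysis is meant to compare subjects who received what they were assigned. Here the set can hold, in its placebo arm, people whom the same SAP treats as exposed to active drug. The converse error, a subject in an active group dosed with another cohort's product, is not screened out either.

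At stake is what the per-protocol result means. If it agrees with ITT, a reader may take that as support for the effect among subjects treated as planned, when the definition never checks product identity. If the drug works, contaminated placebo subjects pull the difference towards zero.

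**Working it through.** **1. The plan's own sample size, for scale (section 3).** Inputs: difference 0.5, SD 1.92, two-sided alpha 0.05, power 90%, dropout 30%.

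n per arm = 2 × (1.960 + 1.282)² × 1.92² / 0.5² ≈ 310 evaluable; 310 / 0.70 ≈ 443, against the planned 450. With 450 × 0.70 = 315 evaluable per arm, power is 90.5%. The plan's figure reproduces. After the increase to 535 per arm, 535 × 0.70 = 374.5 evaluable gives power of 94.6% and a standard error of the difference of 1.92 × √(2 / 374.5) ≈ 0.14.

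**2. Following one subject through the rules.** Take a subject randomized to placebo who received one or more active doses by mistake, had 14 or more infusions in all, met the listed entry criteria and kept AD medication unchanged.

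| Rule | Result |
|---|---|
| 4.1.1 entry criteria | met |
| 4.1.1 infusion count | met; product not considered |
| 4.1.1 AD medication | met |
| 4.3.1 efficacy grouping | placebo, as randomized |
| 4.5.1 safety grouping | low or high dose |

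The subject is in the per-protocol placebo arm for CDR-SB and in an active arm for adverse events.

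**3. Does another efficacy analysis remove them?** Table 2 lists ten analyses of CDR-SB. Nine use the ITT population. Of these, only the censoring analysis (4.3.2.3.1) drops observed data, and only after treatment discontinuation or a change in AD symptomatic medication. Accidental active dosing is neither. The four sensitivity analyses concern missing data. So the per-protocol analysis is the only one whose definition could deal with these subjects, and it does not.

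**4. Size, under assumptions.** The SAP gives no count of such subjects. Let f be the share of placebo subjects affected, each with the full active effect. The expected difference becomes 0.5 × (1 − f). Power uses 374.5 per arm and is indicative only, since the per-protocol set will be smaller and its size is not stated.

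| f (assumed) | Difference | Loss | Power |
|---|---|---|---|
| 0 | 0.5 | 0 | 94.6% |
| 0.5% | 0.4975 | 0.0025 | 94.4% |
| 1% | 0.495 | 0.005 | 94.2% |
| 2% | 0.49 | 0.01 | 93.7% |
| 5% | 0.475 | 0.025 | 92.3% |

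At 2%, the loss is 0.01 / 0.14 ≈ 0.07 of a standard error. The full effect is a generous assumption, because 4.5.1 applies from a single accidental dose. If benefit were proportional to doses (also an assumption), one active dose out of 20 at f = 2% would cost 0.02 × 0.5 × 1/20 = 0.0005.

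**The case against.** The case for leaving the definition alone is fair in several respects. The per-protocol analysis is supplementary and has no part in the multiplicity scheme. The likely dilution is a small fraction of a standard error and, if the drug works, goes against it, so it would not create a false positive. The affected subjects remain visible through the 4.2.5 listing. The SAP does not itself equate the wrong-cohort deviation with placebo subjects given active drug. All of this stands. It limits the weight of the point but does not supply a reason for keeping wrongly dosed subjects in a set meant to exclude them.

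Two stronger readings may tempt a reader, and the SAP supports neither.

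- **That the per-protocol rule is inconsistent because it excludes for a Minor deviation and keeps Major ones.** Appendix 6.2 does rate "Change in AD medications during course of the study" as Minor. But a change in AD symptomatic medication is a named intercurrent event (note to Table 2, 4.3.2.1, 4.3.2.3.1), so the exclusion follows from the efficacy reasoning. The Major and Minor labels serve the monitoring summaries of 4.2.4, and the SAP does not say that they should define analysis sets. The per-protocol rule also removes some Major deviations, namely failures of the listed entry criteria.
- **That ratings affected by "Unblinded information made available to the blinded site personnel" or by "CDR raters were performing other assessments on subjects they performed CDRs for" must be removed.** The first does not say that the CDR rater learned an allocation; the second is a procedural breach, not evidence of a biased score. Dropping ratings from a given date would be a further post-randomization censoring rule, and the SAP does not show that the log supports exclusions at that level. A sensitivity analysis on these would be optional.

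**Conclusion.** The gap is real and narrow. As written, a placebo subject who received active drug can be analysed as per-protocol placebo while counted as active for safety, and no other efficacy analysis sets such a subject aside. This follows from the infusion condition in 4.1.1 taken with the grouping rules in 4.3.1 and 4.5.1, and needs no assumption. Its size does: about 0.01 CDR-SB points at 2% contamination with full effect, and 0.0025 to 0.025 over the 0.5% to 5% range. The effect on the estimate is probably minor, and the primary ITT result is not touched. It is a cheap improvement to a supplementary analysis, not a threat to the trial's conclusion.

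**What to change.** Add a fourth condition to the per-protocol definition in 4.1.1: the subject received no dose of a product other than the one assigned. State that this excludes (a) placebo subjects given any active dose and (b) subjects with the wrong-cohort deviation of Appendix 6.2 who were actually dosed with that product. State also that scheduled titration, dose adjustments made under the protocol's ARIA rules, and the earlier-version carriers whom 4.3.1 already places in the high-dose group do not count as wrong product.

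Identifying these subjects reveals allocation. The list should therefore be drawn up from the dosing records by a function that is already unblinded or independent, and fixed before the study team is unblinded.

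The cost is a few lines of SAP text and a review of records that 4.2.5 already requires to be listed. The downside is a slightly smaller per-protocol set and one more exclusion based on events after randomization. The ITT population and the primary analysis stay as they are.

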4.2 Background Characteristics

The summaries in this section will be based on the ITT population. Unless otherwise specified, summary tables will be presented by treatment group (analysis display A in Appendix 6.1) and by treatment group stratified by ApoE status (analysis display B in Appendix 6.1; here ApoE status refers to the status recorded in IXRS [see Table 1 for correspondence between treatment groups and treatment groups stratified by ApoE status]). All the listings will be presented by treatment group stratified by ApoE status, unless otherwise specified.

Final V1.0

4.2.1 Accounting of Subject

Disposition of subjects will be summarized and the summary data will include number (%) of subjects randomized and dosed, number (%) of subjects who completed the treatment/study, and number (%) of subjects who discontinued treatment and/or withdrew from study. For subjects who discontinued treatment and/or withdrew from study, the reasons for discontinuation and/or withdrawal, and days on treatment and days on study will be summarized and listed. The number of subjects discontinuing treatment prior to each scheduled clinical efficacy assessment will be summarized (presented by treatment group), i.e., the number of subjects discontinuing treatment between Day 1 and Week 26, the number of subjects discontinuing treatment between Week 26 and Week 50 visit, etc. A similar summary will be done for subjects who withdrew from study (presented by treatment group). Time to treatment discontinuation and time to study withdrawal will be displayed by Kaplan-Meier plot (presented by treatment group).

Number of subjects in each analysis population will be summarized. Number of subjects dosed will be summarized by region, country and site. In addition, number of subjects who completed the treatment/study will be summarized by region and country (presented by treatment group).

The categorization of region is based not only on consideration of geography but also on type of health care system and access to health care in each country. This region category will be used in all analysis, including the demographics, the covariate in statistical models and subgroup analysis. The categories for regions will be:

- o Region 1: United States (US);
- o Region 2: European countries (including Austria, Denmark, France, Germany, Italy, Portugal, Spain and United Kingdom), plus Australia and Canada;
- o Region 3: Asia countries (including Japan, South Korea and Taiwan).

4.2.2 Demographics and Baseline Characteristics

The demographic data including age, gender, ethnicity, race, height, weight, and body mass index (BMI) will be summarized. Age will also be categorized and presented using the following two groupings: <50, 50-60, 61-70, 71-80, 81-85, >85 years, and ≤ 64 , 65-74, ≥ 75 .

Summary of the baseline characteristics of AD includes laboratory ApoE ε4 status (carrier or non-carrier), baseline clinical stage (MCI due to AD or mild AD), baseline clinical assessment including RBANS delayed memory index, CDR global score, CDR-SB, CDR cognitive subscore, CDR functional subscore, MMSE, ADAS-Cog 13, ADCS-ADL-MCI, number of years of formal education, number of years since first AD symptom, number of years since diagnosis of AD, AD treatment use that was stopped prior to entering the study (yes or no) and AD symptomatic medication use at baseline (yes or no; see Section 4.2.3 for definition of AD symptomatic medication use at baseline). ApoE ε4 carrier will be further classified as homozygote and heterozygote. MMSE will also be categorized by the following subgroups: <24, 24-26, 27-30. Subject listings will be generated for demographics and baseline characteristics.

Final V1.0

Medical history will be coded using the Medical Dictionary for Regulatory Activities (MedDRA). The number (%) of subjects with history (including both ongoing and not ongoing medical conditions) will be summarized by system organ class and preferred term. A listing of medical history will be generated.

Previous therapies for the treatment of AD stopped prior to entering the study, total duration of previous therapies and reason for stopping treatment will be summarized (presented by treatment group). A listing of previous therapies will also be generated.

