3 SAMPLE SIZE JUSTIFICATION

The study's sample size is based, in part, on results from a protocol-specified interim analysis from Study 221AD103 which included 1 year data from 1, 3 and 10 mg/kg treatment groups.

A sample size of 450 subjects per treatment group (1350 in total) was planned to have approximately 90% power to detect a true mean difference of 0.5 in change from baseline CDR-SB at Week 78 between the 2 treatment groups. This power calculation was based on a 2-sided t-test assuming equal variance with a final significance level of 0.05, a standard deviation (SD) of 1.92 and a drop-out rate of 30%. The SD estimate of 1.92 for Week 78 reflected a 39% increase over the SD from the protocol-specified interim analysis of 1-year data.

The assumed true mean difference of 0.5 between the 2 treatment groups represents an approximately 25% reduction in the placebo mean change from baseline at Week 78 if the placebo mean change is estimated to be 2.

As defined in the protocol, the sample size for this study (and for the identically designed Study 221AD302) was reassessed in a blinded manner in November 2017 (approximately 3 months before enrollment completion and with about 10.6% of the data available on the primary endpoint from Studies 221AD301 and 221AD302 combined). At this timepoint, the SD of the primary endpoint was estimated based on the pooled blinded data from two studies using a modified version of Gould-Shih simple-adjustment one sample variance (Zucker et al. 1999):

$$s_{adj}^2 = s_{os}^2 - \frac{2N}{9(N-1)}\delta^2,$$

where N denotes the number of subjects included in the analysis for blinded sample size reestimation (subjects with both baseline and Week 78 CDR-SB available at the time of sample size re-estimation), δ is the assumed true treatment effect (same treatment effect assumed for both the high dose group and low dose group in this analysis), and s_{os}^2 is the unadjusted one sample variance of the primary endpoint estimate from the pooled blinded data.

As a result of this analysis, the sample size has been increased from 1350 to 1605 (450 to 535 per treatment group) to assure adequate power for detecting a mean treatment effect of 0.5.

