4.3.2 Primary Efficacy Endpoint

4.3.2.1 Primary analysis

The estimand of the primary analysis is the mean difference of the change from baseline CDR-SB scores at Week 78 between treatment groups in the ITT population [ICH E9 (R1) Addendum 2014, 2017]. All observed data will be included in the primary analysis, including data collected after intercurrent events [ICH E9 (R1) Addendum 2017], i.e., treatment discontinuation or a change in concomitant use of AD symptomatic medication.

The change from baseline CDR-SB scores will be summarized by treatment group at each post-baseline visit. A mixed model repeated measures (MMRM) model will be used as the primary analysis to analyze change from baseline CDR-SB using fixed effects of treatment group, time (categorical), treatment group-by-time interaction, baseline CDR-SB, baseline CDR-SB by time interaction, baseline MMSE, AD symptomatic medication use at baseline (yes/no; see Section 4.2.3 for definition of AD symptomatic medication use at baseline),

Final V1.0

region, and laboratory ApoE £4 status (carrier/non-carrier). An unstructured covariance matrix will be used to model the within-patient variance-covariance errors. If the unstructured covariance structure matrix results in a lack of convergence, the heterogeneous Toeplitz covariance structure followed by the heterogeneous first-order autoregressive covariance structure will be used. The Kenward-Roger approximation will be used to estimate the denominator degrees of freedom. In the primary analysis, missing data are assumed to be missing at random [Rubin 1976].

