4.3.2.2.3 Imputation by natural disease progression

Subjects are assumed to exhibit an evolution of the disease similar as the natural disease progression after early withdrawal from study (for all treatment groups). The natural disease progression is determined based on a snapshot of the Alzheimer's Disease Neuroimaging Initiative (ADNI) database [Mueller et al. 2005] obtained in May 2017. A subpopulation was defined that satisfies the major inclusion criteria of Study 221AD301 (and the identically designed Study 221AD302). In this subpopulation, the mean change from baseline CDR-SB at Week 78 is estimated to be about 1.52 for subjects with late mild cognitive impairment (LMCI) and about 2.06 for subjects with mild AD. The missing data at Week 78 for this study will be imputed using the linear extrapolation approach based on subjects' baseline clinical stage (MCI due to AD or mild AD). For example, assuming a mild AD patient whose last non-missing change from baseline CDR-SB measurement is 0.5 at Week 26, the change from baseline CDR-SB at Week 78 for this patient will be imputed as 0.5+2.06*(78-26)/78, which is 1.87. A similar algorithm will be applied to the MCI patients. After imputation, the change from baseline CDR-SB at Week 78 will be analyzed by an ANCOVA model adjusting treatment group, baseline CDR-SB, baseline MMSE, AD symptomatic medication use at baseline (yes/no), region, and laboratory ApoE & status (carrier/non-carrier).

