4.3.5 Subgroup Analysis

Subgroup analyses will be performed for the primary endpoint (CDR-SB) and secondary endpoints (MMSE, ADAS-Cog13, ADAS-ADL-MCI). The following pre-defined subgroups will be considered:

- Laboratory ApoE & status (carrier or non-carrier)
- Baseline clinical stage (MCI due to AD or mild AD) per the Investigator's assessment based on the National Institute on Aging-Alzheimer's Association (NIA-AA) criteria
- Use of AD symptomatic medication at baseline (yes or no)

Final V1.0

- Baseline MMSE (MMSE \leq 26 or MMSE \geq 27)
- Region (US, Europe/Canada/Australia, Asia; see Section 4.2.1 for definition of region)
- Age category ($\leq 64, 65-74, \geq 75$)
- Gender (female or male)

A selective set of subgroup analyses will be performed for Amyloid PET data. Details will be defined in Sections 4.4.

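### Clinical stage sets the imputed Week 78 decline in SAP 4.3.2.2.3 but is not a covariate in that ANCOVA or in the primary MMRM; adding it is a small, nearly free gain in precision

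*SAP*

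**What the plan says.** Stage appears in three roles in the SAP.

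- Section 4.2.2 summarises it at baseline: "baseline clinical stage (MCI due to AD or mild AD), baseline clinical assessment including RBANS delayed memory index".
- Section 4.3.5 makes it a pre-defined subgroup factor for the primary and secondary endpoints: "Baseline clinical stage (MCI due to AD or mild AD) per the Investigator's assessment", on NIA-AA criteria.
- Section 4.3.2.2.3 uses it to impute missing Week 78 values after early withdrawal. The mean Week 78 change in an external natural-history subpopulation is "estimated to be about 1.52 for subjects with late mild cognitive impairment (LMCI) and about 2.06 for subjects with mild AD", and each subject's remaining follow-up is filled in linearly at the rate for his or her stage.

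Stage is absent elsewhere. Section 2.1 stratifies randomisation by ApoE ε4 carrier status and site. The primary MMRM in section 4.3.2.1 has "fixed effects of treatment group, time (categorical), treatment group-by-time interaction, baseline CDR-SB, baseline CDR-SB by time interaction, baseline MMSE", followed by symptomatic AD medication use, region and laboratory ApoE ε4 status. The ANCOVA in 4.3.2.2.3 adjusts for treatment and the same baseline factors, again without stage.

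**The concern.** By its imputation rule the SAP treats stage as a predictor of decline. A baseline factor that is known to be prognostic, already recorded and not balanced by the randomisation would normally go into the model. Left out, any stage-related decline that the other covariates miss stays in the residual variance.

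The mismatch is plainest inside 4.3.2.2.3. There the imputed part of the outcome is a fixed function of stage, but the model that analyses it cannot see stage.

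A further argument is conditional. The primary analysis assumes data missing at random, and if withdrawal depended on stage, conditioning on stage would make that assumption easier to defend. The SAP does not say whether withdrawal depends on stage.

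**Working it through.** **Inputs.** Section 3 gives "90% power to detect a true mean difference of 0.5 in change from baseline CDR-SB at Week 78", with "final significance level of 0.05, a standard deviation (SD) of 1.92 and a drop-out rate of 30" per cent. It also gives "A sample size of 450 subjects per treatment group (1350 in total) was planned" and a later increase to 535 per group. Section 4.3.2.2.3 gives 1.52 and 2.06. The mild AD share p is not stated, so 20% to 50% is assumed; 50% gives the largest possible stage variance.

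**Reproducing the plan's figure.** Evaluable n per group = 2 × (1.960 + 1.282)² × 1.92² / 0.5² = 310. Dividing by 0.7 gives 443, close to the planned 450. With 450 × 0.7 = 315 evaluable per group, the standard error is 1.92 × √(2/315) = 0.153 and power is 90.5%. The stated figure is reproduced.

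**Gap between stages.** 2.06 − 1.52 = 0.54 points, or 0.54 / 1.92 = 0.28 SD.

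**Variance that stage could explain.** Stage variance is p(1 − p) × 0.54², and the adjusted SD is √(1.92² − p(1 − p) × 0.54²). Power is Φ(0.5 / (SD × √(2/n)) − 1.96).

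| Mild AD share | Stage variance | Share of 1.92² | Adjusted SD | Power, n = 315 | Power, n = 374.5 |
|---|---|---|---|---|---|
| no adjustment | – | – | 1.920 | 90.5% | 94.6% |
| 20% | 0.0467 | 1.3% | 1.908 | 90.8% | 94.8% |
| 30% | 0.0612 | 1.7% | 1.904 | 90.9% | 94.9% |
| 50% | 0.0729 | 2.0% | 1.901 | 91.0% | 94.9% |

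The last column uses 535 × 0.7 = 374.5 evaluable per group, still at SD 1.92. For 90% power, the required size per group falls from 443 to between 438 (20%) and 435 (50%).

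**After the covariates already in the model.** The table credits the full unadjusted gap to stage, so it is an upper bound. If baseline CDR-SB and MMSE absorb half the gap (an assumption), 0.27 points remain. The share is then 0.16 × 0.27² / 1.92² = 0.3% at p = 20% and 0.25 × 0.27² / 1.92² = 0.5% at p = 50%, worth about 0.1 percentage points of power.

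**Chance imbalance.** The SD of the difference in stage share between two arms is √(2p(1 − p)/315), which is 3.2 percentage points at p = 20% and 4.0 at p = 50%. The 95% limits are 6.2 (1.96 × 3.19) and 7.8 points. Multiplied by 0.54, they move the treatment difference by 0.034 and 0.042 points, against the standard error of 0.153. A shift of 0.1 points would need an imbalance of 0.1 / 0.54 = 18.5 percentage points.

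**The ANCOVA in 4.3.2.2.3.** For a subject last seen at Week 26, the imputation builds in a stage difference of 0.54 × 52/78 = 0.36 points. With no post-baseline visit and the rule run from baseline, it is the full 0.54. This holds whatever the mild AD share.

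**The case against.** The case for leaving the model as it is has real force. It already adjusts for severity with two scale scores, one of them interacting with time, and stage is a two-level investigator judgement that overlaps with them. Preferring scores to a label is a legitimate choice. Stage is also summarised by arm and examined as a subgroup, so an imbalance would be seen. All of this stands, and it is why the point is minor.

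Three stronger readings are tempting, and the SAP supports none of them.

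- A reader might infer from 0.54 exceeding 0.5 that stage could swamp the drug effect. Lost precision depends on p(1 − p) × 0.54² relative to the outcome variance, not on that comparison.
- A reader might infer that a chance imbalance biases the result. Under randomisation it is random error, already reflected in the standard error, and the severity covariates take up part of it.
- A reader might infer that the 4.3.2.2.3 analysis favours an arm. The stage-specific rates apply alike to every treatment group, so omitting the stage term favours none.

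The missing-at-random argument stays conditional. The MMRM also conditions on each subject's observed CDR-SB, and four sensitivity analyses address departures from the assumption.

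**Conclusion.** The omission is real, but it is not an error in the primary analysis and causes no bias. Adjusting for stage would remove at most about 2% of the Week 78 variance, worth at most about 0.5 percentage points of power at the planned size and less at 535 per group. The true gain is probably smaller. It is a minor, free improvement; the internal mismatch in 4.3.2.2.3 is its clearest part.

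This rests on four assumptions: a mild AD share of 20% to 50%; the planning SD of 1.92 (stage would reach 5% at p = 50% only if the SD fell to √(0.0729/0.05) = 1.21); the external late MCI group as a stand-in for MCI due to AD in this trial; and an unadjusted gap, since the SAP gives none after adjustment for baseline scores.

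**What to change.** Before unblinding:

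- add baseline clinical stage as a covariate to the ANCOVA in 4.3.2.2.3;
- add stage and stage-by-time to the fixed effects of the CDR-SB MMRM in 4.3.2.1 or, at minimum, pre-specify that model as a sensitivity analysis;
- make the same change for the identically designed Study 221AD302.

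The cost is SAP wording, agreement across the two studies, one degree of freedom in the ANCOVA and three in the MMRM (one for stage, two for its interaction with three visits). No new data are needed. Made after unblinding, the same change would look post hoc.

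Extending it to MMSE, ADAS-Cog 13 and ADCS-ADL-MCI is optional, because the SAP gives no stage figures for those scales. For ADCS-ADL-MCI the primary analysis pools both studies, so the two plans would have to change together.
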